Protocol I5B-JE-JGDK (b)

A Phase 1 Study of Olaratumab in Japanese Patients with Advanced Soft Tissue Sarcoma or Advanced Solid Tumors

NCT02377752

Approval Date: 28-Sep-2018

1. Protocol I5B-JE-JGDK (b)

A Phase 1 Study of Olaratumab in Japanese Patients with Advanced Soft Tissue Sarcoma or Advanced Solid Tumors

Confidential Information

The information contained in this protocol is confidential and is intended for the use of clinical investigators. It is the property of Eli Lilly and Company or its subsidiaries and should not be copied by or distributed to persons not involved in the clinical investigation of olaratumab (LY3012207), unless such persons are bound by a confidentiality agreement with Eli Lilly and Company or its subsidiaries. This document and its associated attachments are subject to United States Freedom of Information Act (FOIA) Exemption 4. Note to Regulatory Authorities: this document may contain protected personal data and/or commercially confidential information exempt from public disclosure. Eli Lilly and Company requests consultation regarding release/redaction prior to any public release.

Olaratumab (LY3012207)

This Phase 1 study is a multicenter, nonrandomized, open-label study to evaluate intravenous olaratumab in combination with doxorubicin in Japanese patients with advanced soft tissue sarcoma or advanced solid tumors (Part A), and intravenous olaratumab alone in Japanese patients with advanced solid tumors (Part B).

Eli Lilly Japan KK
Kobe, Hyogo, Japan

Protocol Approved by Lilly: 09 Dec 2014
Amendment (a) Protocol Electronically Signed and Approved by Lilly on 26 Jun 2015
Amendment (b) Protocol Electronically Signed and Approved by Lilly on date provided below.

Approval Date: 28-Sep-2018 GMT

2. Synopsis

Name of Investigational Product: Olaratumab	
Title of Study: A Phase 1 Study of Olaratumab in Japanese Patients with Advanced Soft Tissue Sarcoma or Advanced Solid Tumors	
Number of Planned Patients/Subjects: Enrolled: 24	Phase of Development: 1
Length of Study: First patient enrolled (assigned to therapy): March 2015 Estimated last patient visit: March 2019	

Objectives: The primary objective of Part A is to evaluate the safety and tolerability of olaratumab in combination with doxorubicin in Japanese patients with advanced solid tumors, especially advanced soft tissue sarcoma.
 
The primary objective of Part B is to evaluate the pharmacokinetics (PK) profile of olaratumab in Japanese patients with advanced solid tumors.
 
The secondary objectives of Part A are:
 
 • To evaluate the PK of olaratumab and doxorubicin • To evaluate the immunogenicity of olaratumab • To document any antitumor activity of olaratumab in combination with doxorubicin 
The secondary objectives of Part B are:
 
 • To evaluate the safety and tolerability of olaratumab • To evaluate the immunogenicity of olaratumab • To document any antitumor activity of olaratumab 
The exploratory objective of Part A and Part B is to evaluate potentially relevant biomarkers related to the mechanism of olaratumab, the platelet-derived growth factor (PDGF) signaling pathway, and the pathobiology of cancer.
	

othersomeIStudy Design: This study is a multicenter, non-randomized, open-label Phase 1 study consisting of 2 parts (Part A and Part B). Part A and Part B will be conducted in parallel.
 
Part A is designed to evaluate the safety and tolerability of olaratumab in combination with doxorubicin in Japanese patients with advanced solid tumors, especially advanced soft tissue sarcoma. This part consists of 3 cohorts. After the first 3 patients from Cohort 1 are enrolled, Cohort 2 can be opened based on safety assessment and after discussion between the investigator, the sponsor, and the Safety Assessment Committee. Cohort 3 can be opened after confirmation of tolerability in Cohort 2.
 
At least 6 patients will be assigned to each cohort and will receive the combination therapy of olaratumab and doxorubicin. One cycle is defined as 21 days, and the combination therapy will continue up to 6 cycles or until the cumulative dose of doxorubicin reaches 500 mg/m², whichever comes later.
 
Patients may continue to receive treatment until progressive disease, the development of unacceptable toxicity, noncompliance or withdrawal of consent by the patient, or investigator decision. If doxorubicin is discontinued, olaratumab monotherapy can be continued in the absence of progressive disease or other discontinuation criteria. For patients who discontinue olaratumab therapy during the first 6 cycles, doxorubicin may be continued (for up to 6 cycles or until the cumulative dose of doxorubicin reaches 500 mg/m², whichever comes later), provided no discontinuation criteria are met.
	

Part B is designed to evaluate the PK profile of olaratumab monotherapy in Japanese patients with advanced solid tumors. This part consists of 1 dose level. At least 6 patients will be assigned and receive the treatment of olaratumab. One cycle is defined as 21 days, and the treatment will continue until progressive disease or meeting other discontinuation criteria.

Diagnosis and Main Criteria for Inclusion and Exclusion:**Part A**

Japanese patients with advanced solid tumors, especially advanced soft tissue sarcoma which are not amenable to surgery and radiotherapy, and who are appropriate candidates for combination therapy of olaratumab and doxorubicin.

Part B

Japanese patients with advanced solid tumors who are appropriate candidates for olaratumab monotherapy after available standard therapies have failed to provide clinical benefit for their disease.

Investigational Product, Dosage, and Mode of Administration or Intervention:**Part A**

- Cohort 1: 15 mg/kg of olaratumab on Day 1 and Day 8, and 25 mg/m² of doxorubicin on Day 1, Day 2, and Day 3 of every 21-day cycle.
- Cohort 2: 15 mg/kg of olaratumab on Day 1 and Day 8, and 75 mg/m² of doxorubicin on Day 1 of every 21-day cycle.
- Cohort 3: 20 mg/kg loading dose of olaratumab on Day 1 and Day 8 in Cycle 1, followed by 15 mg/kg on Day 1 and Day 8 in subsequent cycles, and 75 mg/m² of doxorubicin on Day 1 of every 21-day-cycle.

Part B

This part consists of 1 dose level: 15 mg/kg of olaratumab on Day 1 and Day 8 of every 21-day cycle.

Planned Duration of Treatment:

Patients will be on treatment until one of the discontinuation criteria is met.

Treatment period: 21 days/cycle

Follow-up Period: 28 days

Criteria for Evaluation:

Safety: Dose-limiting toxicities, treatment-emergent adverse events (TEAEs) using Common Terminology Criteria for Adverse Events (CTCAE) version 4.03 and the Medical Dictionary for Regulatory Activities (MedDRA), laboratory evaluations, vital signs, electrocardiograms and cardiac function as measured by echocardiogram.

Bioanalytical: Serum concentrations of olaratumab (Part A and B) and plasma concentrations of doxorubicin (Part A).

Pharmacokinetics: The primary parameters for analysis will be maximum observed concentration (C_{max}) and area under the concentration-time curve (AUC) from time 0 to the last time point with a measurable concentration, and AUC from time 0 to infinity of olaratumab and doxorubicin. Other noncompartmental parameters, such as half-life, clearance, and volume of distribution, may be reported.

Efficacy: Antitumor activity according to Response Evaluation Criteria in Solid Tumors version 1.1.

Biomarkers: Biomarkers related to the mechanism of olaratumab, the PDGF signaling pathway, and the pathobiology of cancer.

Statistical Methods:

Safety: Dose-limiting toxicities will be listed and summarized by frequency. Adverse events (AEs), including TEAEs, will be listed and summarized in frequency tables using MedDRA. Severity of AEs will be classified using CTCAE version 4.03. Other safety data, such as laboratory tests, echocardiography, and vital signs, will be listed and summarized, if appropriate.

Efficacy: Efficacy data will be listed. Also, efficacy data will be summarized using frequency table or summary statistics, depending on the characteristics of the data.

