6.2. Summary of Study Design

This is a multicenter, nonrandomized, open-label, Phase 1 study. The study is divided into 2 parts, Part A and Part B. Part A and Part B will be conducted in parallel. The DLT evaluation of Cohort 1, 2 and 3 in Part A will be performed independently. The study design is summarized in Figure JGDK.6.1.

Refer to [Attachment 1](#) for the Study Schedule.

Abbreviations: ECOG = Eastern Cooperative Oncology Group; PS = performance score; D= day; N = number of patients; LVEF = left ventricular ejection fraction

^a For patients whose cumulative dose of doxorubicin does not reach 500 mg/m^2 during the first 6 cycles due to dose reductions or omissions, doxorubicin can be administrated up to 500 mg/m^2 on Cycle 7 and beyond, at the discretion of the investigator.

^b Refer to Section [7.2.1.4](#) for the timing to open Cohort 2 and 3.

[figure not shown]
Figure JGDK.6.1. Illustration of study design for Protocol I5B-JE-JGDK.

Part A is designed to evaluate the safety and tolerability of olaratumab in combination with doxorubicin in Japanese patients with advanced solid tumors, especially advanced STS.

Part A consists of 3 cohorts (Figure JGDK.6.1). At least 6 patients will be assigned to Cohort 1. Similarly, at least 6 patients will be assigned to Cohort 2 and 3:

- Cohort 1: 15 mg/kg of olaratumab on Day 1 and Day 8, and 25 mg/m² of doxorubicin on Day 1, Day 2, and Day 3 up to 6 cycles or until when cumulative dose of doxorubicin reaches 500 mg/m², whichever comes later, every 21 day-cycle.
- Cohort 2: 15 mg/kg of olaratumab on Day 1 and Day 8, and 75 mg/m² of doxorubicin on Day 1 up to 6 cycles or a cumulative dose of doxorubicin reaches 500 mg/m², whichever comes later, every 21 day-cycle.
- Cohort 3: 20 mg/kg loading dose of olaratumab on Day 1 and Day 8 in Cycle 1, followed by 15 mg/kg on Day 1 and Day 8 in subsequent cycles, and 75 mg/m² of doxorubicin on Day 1 up to 6 cycles or a cumulative dose of doxorubicin reaches 500 mg/m², whichever comes later, every 21 day-cycle.

An overview of the study design for Part A is shown in Figure JGDK.6.2.

[figure not shown]

Abbreviations: DLT = dose-limiting toxicity; IC = informed consent; n = number; N = no; Y = yes.

Figure JGDK.6.2. Illustration of study schedule in Part A.

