7.2.1. Dosing Schedule

The dosing schedule and mode of administration are summarized in [Table JGDK.7.1](#).

Table JGDK.7.1. Dosing Regimens (21-day cycles)

	Drug	Treatment	Day	Infusion duration
Part A	Cohort 1	Olaratumab ^a	15 mg/kg I.V. infusion	Days 1 and 8 Approximately 60 minutes
		Doxorubicin ^{a,b}	25 mg/m ² I.V. infusion	Days 1, 2, 3 Approximately 30 minutes
Part A	Cohort 2	Olaratumab ^a	15 mg/kg I.V. infusion	Days 1 and 8 Approximately 60 minutes
		Doxorubicin ^{a,b}	75 mg/m ² I.V. infusion	Days 1 Approximately 30 minutes
	Cohort 3	Olaratumab ^a	20 mg/kg I.V. infusion 15 mg/kg I.V. infusion	Days 1 and 8 in Cycle 1 Days 1 and 8 in Cycle 2 and beyond Approximately 60 minutes Approximately 60 minutes
Part B	Doxorubicin ^{a,b}	75 mg/m ² I.V. infusion	Days 1	Approximately 30 minutes
	Olaratumab	15 mg/kg I.V. infusion	Days 1 and 8	Approximately 60 minutes

Abbreviation: I.V. = intravenous.

^a Doxorubicin will be administered approximately 1 hour after the completion of the olaratumab infusion on the days when both olaratumab and doxorubicin are administered.

^b Doxorubicin administration in each 21-day cycle up to 6 cycles or until when a cumulative dose reaches 500 mg/m², whichever comes later.

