7.2.1.2. Doxorubicin

In Part A only, all patients will receive 25 mg/m² of doxorubicin on Day 1/2/3 (Cohort 1) or 75 mg/m² of doxorubicin on Day 1 (Cohort 2 and 3) of each 21-day cycle, administered as an intravenous infusion over approximately 30 minutes. Doxorubicin will be administered for up to 6 cycles until progressive disease or meeting the other discontinuation criteria. For patients whose cumulative dose of doxorubicin does not reach 500 mg/m² during the first 6 cycles (because of dose reductions or omissions), doxorubicin can be administered up to 500 mg/m² at the following cycles at the discretion of the investigator. On the days when both olaratumab and

doxorubicin are administered, doxorubicin will be administered approximately 1 hour after the completion of the olaratumab infusion.

If a patient completes 6 cycles, olaratumab monotherapy can be continued in the absence of disease progression or other discontinuation criteria.

If doxorubicin is discontinued (eg, for reasons of toxicity), olaratumab monotherapy can be continued. For patients who discontinue olaratumab during the first 6 cycles of treatment, doxorubicin may be continued (for up to 6 cycles or up to 500 mg/m² at the discretion of the investigator).

The dose of doxorubicin will be calculated using body surface area and is dependent upon the patient's baseline height in centimeters. A change of weight $\geq 10\%$ from baseline will result in re-calculation of doxorubicin dose to be administered based on body surface area.

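### Part A limits doxorubicin by two rules that disagree, and the one stated most often treats 500 mg/m² as a point to reach, not a ceiling

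*Protocol*

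**What the plan says.** The later-of rule. The Synopsis states it twice, once for the combination ("the combination therapy will continue up to 6 cycles or until the cumulative dose of doxorubicin reaches 500 mg/m², whichever comes later") and once for patients who stop olaratumab early ("doxorubicin may be continued (for up to 6 cycles or until the cumulative dose of doxorubicin reaches 500 mg/m², whichever comes later"). Each of the three cohort bullets in Protocol Section 6.2 repeats it. For Cohorts 2 and 3 the wording is "75 mg/m² of doxorubicin on Day 1 up to 6 cycles or a cumulative dose of doxorubicin reaches 500 mg/m², whichever comes later". Footnote b to Table JGDK.7.1, inside the dosing section, reads "Doxorubicin administration in each 21-day cycle up to 6 cycles or until when a cumulative dose reaches 500 mg/m², whichever comes later". SAP Section 5.1 carries it in both of its cohort bullets.

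The capped rule. Section 7.2.1.2 gives doxorubicin for up to 6 cycles. It then covers patients who have not reached 500 mg/m² by that point: "because of dose reductions or omissions), doxorubicin can be administered up to 500 mg/m² at the following cycles", at the investigator's discretion. It adds "If a patient completes 6 cycles, olaratumab monotherapy can be continued in the absence of disease progression or other discontinuation criteria". For patients who stop olaratumab early it says "for up to 6 cycles or up to 500 mg/m² at the discretion of the investigator", with no later-of clause. Footnote a to Figure JGDK.6.1 agrees: "due to dose reductions or omissions, doxorubicin can be administrated up to 500 mg/m^2 on Cycle 7 and beyond". Footnote a to SAP Figure JGDK.5.1 says the same.

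The reference figure. Section 5.5 gives 500 mg/m² as the maximum cumulative dose on the Japanese label and ties it to myocardial damage.

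**The concern.** The two rules can give the same patient different amounts of a cardiotoxic drug, in a part of the study whose primary objective is safety and tolerability. No section says which rule governs. A site that turns to the dosing section finds both: the later-of rule in the table footnote and the capped rule in Section 7.2.1.2. Section 6.2 and SAP Section 5.1 also each carry both.

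The protocol itself treats cumulative dose as important. Sections 5.1 and 5.4 report more cardiotoxicity with the combination in the earlier randomized sarcoma study (14.1% against 9.2%) and attribute it to more doxorubicin cycles and a higher cumulative dose. A rule that tells sites to continue until 500 is reached, without saying that the last dose must be cut to fit, can carry a patient past the limit the protocol cites.

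**Working it through.** Inputs: 75 mg/m² per cycle in every cohort (3 × 25 in Cohort 1, a single 75 in Cohorts 2 and 3; Table JGDK.7.1). Reduced levels of about 60 and then 45 mg/m², with no re-escalation (Table JGDK.7.3, Section 7.2.2.2). Maximum of 500 mg/m² (Section 5.5). The 500 is a label figure, so there is no calculation in the plan to reproduce.

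1. Count of later-of statements: Synopsis 2 + Section 6.2 3 + Table JGDK.7.1 1 + SAP Section 5.1 2 = 8.

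2. Which limit comes later? Six full cycles give 6 × 75 = 450 mg/m², which is 500 − 450 = 50 short. Reaching 500 in six cycles would need 500 / 6 = 83.3 mg/m² per cycle. So reaching 500 is always the later event and the 6-cycle limit never operates.

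3. Cumulative dose (mg/m²) in Cohorts 2 and 3, giving whole doses until 500 is reached:

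| Patient | After Cycle 6 | Cycle 7 | Cycle 8 | Cycle 9 | Limit under the capped rule |
|---|---|---|---|---|---|
| Full dose throughout | 450 | 450 + 75 = 525, stop | – | – | 450 or 500, depending on the reading in step 6 |
| 75 in Cycle 1, then 60 | 75 + 5 × 60 = 375 | 435 | 495 | 495 + 60 = 555, stop | 500 (at most 5 in Cycle 9) |

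   Relative excess: 525 / 500 = 1.05 and 555 / 500 = 1.11.

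4. Range over reduction paths. With doses of 75, 60 and 45, every total is a multiple of 15. The first multiple at or above 500 is 510 (for example 6 × 75 + 60, in Cycle 7). The largest overshoot is 495 + 60 = 555. Enumerating all non-increasing 75/60/45 paths that start at 75 gives 510 to 555, reached in Cycles 7 to 11.

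5. Cohort 1 at full dose: 450 + 25 (Cycle 7 Day 1) + 25 (Cycle 7 Day 2) = 500. If the total is checked before each infusion, the later-of rule lands exactly on 500. The overshoot at full dose is therefore a Cohort 2 and 3 matter.

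6. What remains open in the capped rule. Section 7.2.1.2 mentions reductions or omissions in parentheses. If this restricts who may continue, a full-dose patient stops at 450. If it only explains why a patient might be short, that patient may receive 50 more. Section 7.2.2.1 describes doxorubicin in Cycle 7 or later for patients below 500 after six cycles without that condition, and a full-dose patient at 450 fits the description. The Attachment 1 doxorubicin row is blank from Cycle 7 onward, although both rules allow some patients to be dosed there.

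I use no path with an omitted cycle. Attachment 5 shows doxorubicin discontinued after a cycle (Cycles 2 to 5) in which it was omitted altogether, so such a patient may never reach Cycle 7 on the drug.

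**The case against.** The strongest reply is that the texts can be read together. Section 7.2.1.2 is the text specific to doxorubicin; it limits the total to 500 twice, and the figure footnotes do so again. Section 5.5 calls 500 a maximum. The later-of wording sets a stopping point and nowhere demands a whole last dose. A careful site would go no higher than 500, and the only open question would be whether a full-dose patient may go from 450 to 500.

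Much of this stands. A reader might infer that the protocol has no cap, or that dosing is open-ended. The documents support neither: the cap exists in Section 7.2.1.2, and under the later-of rule the excess is at most part of one dose. What does not stand is that the cap clearly prevails. Eight statements omit it, one of them in the dosing section itself, and no order of precedence is given.

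Safeguards also limit the consequence. Prior anthracyclines and mediastinal or pericardial radiation are excluded, baseline LVEF must be at least 50%, doxorubicin stops on set LVEF falls, and an echocardiogram is due before Cycle 7. These respond to cardiac findings and do not limit dose. After Cycle 7 the next scheduled echocardiogram is at follow-up, although one may be done when clinically indicated. The patient who crosses 500 in Cycle 9 has none scheduled just before that dose.

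**Conclusion.** Wrong as written. The two statements of the limit disagree, and the more frequent one does not make 500 mg/m² a ceiling. Followed literally in Cohorts 2 and 3, it gives 525 mg/m² at full dose and up to 555 on a reduction path, 5% and 11% above the cited maximum. These figures assume whole doses, the 75/60/45 levels of Table JGDK.7.3 (whose 60 is approximate), and a patient still on doxorubicin after Cycle 6.

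A reader might infer that the tolerability conclusion is compromised. It is not: DLTs are counted in Cycle 1 only, long before either limit applies. Nor can a size of harm be claimed, because the documents give no risk figure for 450, 500, 525 or 555 mg/m². They also do not settle whether 450 or 500 was intended for a full-dose patient; that is a treatment decision for the sponsor.

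**What to change.** Replace the later-of wording in all eight places with one rule: cumulative doxorubicin must not exceed 500 mg/m², and the last dose is reduced or withheld to stay within it. The sponsor should state whether a full-dose patient stops at 450 mg/m² or may receive up to 50 mg/m² more at the investigator's discretion. Sections 7.2.1.2 and 7.2.2.1 and the Attachment 1 doxorubicin row for Cycle 7 onward should then be aligned with that choice.

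The documents do not say whether any patient still receives doxorubicin. If none does, correct the text and report which rule was applied. SAP Section 6.11.1 already lists cumulative doxorubicin dose per patient, so this needs no new data.

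The cost is a wording change in the protocol and SAP and a clarification to sites. It adds no patients, visits or procedures.

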Attachment 2.	Protocol I5B-JE-JGDK Clinical Laboratory Tests.....	71
Attachment 3.	Protocol I5B-JE-JGDK Hepatic Monitoring Tests for Treatment-Emergent Abnormality	72
Attachment 4.	Protocol I5B-JE-JGDK Pharmacokinetic Sampling, ECG, and Immunogenicity Sampling Schedule	73
Attachment 5.	Protocol I5B-JE-JGDK Olaratumab and Doxorubicin Dosing Scenarios for Dose Delay and Omission	82
Attachment 6.	Protocol I5B-JE-JGDK Recommendations for Reporting Serious Adverse Events	88
Attachment 7.	Protocol I5B-JE-JGDK Creatinine Clearance Formula.....	89
Attachment 8.	Protocol I5B-JE-JGDK NCI-CTCAE (v4.03) Infusion-Related Reactions	90
Attachment 9.	Protocol I5B-JE-JGDK (b) Amendment Summary A Phase 1 Study of Olaratumab in Japanese Patients with Advanced Soft Tissue Sarcoma or Advanced Solid Tumors	91

4. Abbreviations and Definitions

Term	Definition
ADA	antidrug antibodies
AE	Adverse event: Any untoward medical occurrence in a patient or clinical investigation subject administered a pharmaceutical product that does not necessarily have a causal relationship with this treatment. An AE can therefore be any unfavorable and unintended sign (including an abnormal laboratory finding), symptom, or disease temporally associated with the use of medicinal (investigational) product, whether or not related to the medicinal (investigational) product.
Akt	protein kinase B
ALT	alanine aminotransferase
ANC	absolute neutrophil count
ASCO	American Society of Clinical Oncology
AST	aspartate aminotransferase
AUC_[0-96hr]	area under the concentration-time curve from time zero to hour 96
AUC_[0-168hr]	area under the concentration-time curve from time zero to hour 168
AUC_(0-t_{last})	area under the concentration-time curve from time zero to the last time point with a measurable concentration
audit	A systematic and independent examination of the study-related activities and documents to determine whether the evaluated study-related activities were conducted, and the data were recorded, analyzed, and accurately reported according to the protocol, applicable standard operating procedures (SOPs), good clinical practice (GCP), and the applicable regulatory requirement(s).
CIOMS	Council for International Organizations of Medical Sciences
C_{max}	maximum observed concentration
C_{max,ss}	maximum observed concentration at steady state
C_{min}	minimum observed concentration
C_{min,ss}	minimum observed concentration at steady state
CL	clearance
CNS	central nervous system
collection database	A computer database where clinical trial data are entered and validated.

complaint	Any written, electronic, or oral communication that alleges deficiencies related to the identity, quality, purity, durability, reliability, safety, effectiveness, or performance of a drug or drug delivery system.
compliance	Adherence to all the study-related requirements, good clinical practice (GCP) requirements, and the applicable regulatory requirements.
confirmation	A process used to confirm that laboratory test results meet the quality requirements defined by the laboratory generating the data and that Lilly is confident that results are accurate. Confirmation will either occur immediately after initial testing or will require that samples be held to be retested at some defined time point, depending on the steps required to obtain confirmed results.
CR	complete response
CRF/eCRF	case report form/electronic case report form: Sometimes referred to as clinical report form, a printed or electronic form for recording study participants' data during a clinical study, as required by the protocol.
CRP	clinical research physician
CRS	clinical research scientist
CT	computed tomography
CTCAE	Common Terminology Criteria for Adverse Events
DLT	dose-limiting toxicity
DNA	deoxyribonucleic acid
ECG	electrocardiogram
ECOG	Eastern Cooperative Oncology Group
end of trial	End of trial is the date of the last visit or last scheduled procedure for the last patient.
enroll	Patients who are enrolled in the trial are those who were confirmed to be eligible and have been assigned to a treatment.
enter	Patients who are entered in the trial are those who have signed the informed consent form directly or through their legally acceptable representatives.
ERB/IRB	ethical review board/institutional review board: /A board or committee (institutional, regional, or national) composed of medical and nonmedical members whose responsibility is to verify that the safety, welfare, and human rights of the patients participating in a clinical study are protected.
GCP	good clinical practice
G-CSF	granulocyte colony stimulating factors
HBV	hepatitis B virus

HCV	hepatitis C virus
IB	Investigator's Brochure
ICF	informed consent form
ICH	International Conference on Harmonisation
IgG1	immunoglobulin G subclass 1
Informed consent	A process by which a patient voluntarily confirms his or her willingness to participate in a particular trial, after having been informed of all aspects of the trial that are relevant to the patient's decision to participate. Informed consent is documented by means of a written, signed and dated informed consent form.
INR	international normalized ratio
interim analysis	An analysis of clinical study data that is conducted before the final reporting database is authorized for data lock.
investigational product	A pharmaceutical form of an active ingredient or placebo being tested or used as a reference in a clinical trial.
investigator	A person responsible for the conduct of the clinical study at a study site. If a study is conducted by a team of individuals at a study site, the investigator is the responsible leader of the team and may be called the principal investigator.
legal representative	An individual, judicial, or other body authorized under applicable law to consent on behalf of a prospective patient, to the patient's participation in the clinical study.
Lilly Safety System	Global safety database that tracks and reports serious adverse and spontaneous events occurring while using a drug/drug delivery system.
LVEF	left ventricular ejection fraction
MAPK	mitogen-activated protein kinase
MedDRA	Medical Dictionary for Regulatory Activities
monitor	A person responsible for ensuring the investigator site complies with the monitoring plan, applicable local SOPs (if any), and global Medical SOPs. Monitors are trained on the investigational product(s), the protocol, informed consent document, any other written information provided to subjects, relevant SOPs, International Conference on Harmonisation Good Clinical Practice guidelines (ICH-GCP), and all applicable laws (for example, privacy and data protection) and regulations.
MRI	magnetic resonance imaging
NCI	National Cancer Institute
NOAEL	no-observable-adverse-effects levels

open-label	A study in which there are no restrictions on knowledge of treatment allocation, therefore the investigator and the study participants are aware of the drug therapy received during the study.
patient	A subject with a defined disease.
PDGF	platelet-derived growth factor
PDGFRα	platelet-derived growth factor receptor α
PDGFRβ	platelet-derived growth factor receptor β
PK	pharmacokinetic(s)
PR	partial response
PS	performance status
RECIST	Response Evaluation Criteria in Solid Tumors
reporting database	A point-in-time copy of the collection database. The final reporting database is used to produce the analyses and output reports for interim or final analyses of data.
SAC	Safety Assessment Committee
SAE	serious adverse event
screen	The act of determining if an individual meets minimum requirements to become part of a pool of potential candidates for participation in a clinical trial.
screen failure	A patient who does not meet one or more criteria required for participation in a trial
SD	Stable disease
sponsor	The party who takes responsibility for the initiation, management and/or financing of a clinical study.
STS	soft tissue sarcoma
SUSAR	suspected unexpected serious adverse reaction
$t_{1/2}$	half-life
TEAE	treatment-emergent adverse event
TK	toxicokinetic(s)
TPO	third-party organization
ULN	upper limit of normal
V	volume of distribution
VEGF	vascular endothelial growth factor

VEGFR

vascular endothelial growth factor receptor

A Phase 1 Study of Olaratumab in Japanese Patients with Advanced Soft Tissue Sarcoma or Advanced Solid Tumors

5. Introduction

